Our preliminary study of cerebral blood flow utilizing SPECT imaging during Tibetan Buddhist meditation demonstrated a number of complex changes including relatively increased cerebral blood flow (CBF) in the prefrontal cortex, the orbitofrontal cortex, and cingulate gyrus, and relatively decreased CBF in the superior parietal region. The results from this study supported the basic hypotheses in this proposal in that there was increased activity in the structures underlying attention and memory processes (Frith 1991). Furthermore, a study by Lazar et al (2005) demonstrated that experienced practitioners of Insight meditation demonstrated increased cortical thickness in the prefrontal cortex when compared to controls. One potential implication is that meditation practice induces long term changes in the brain, but this has not been widely studied on a functional level. Furthermore, functional changes in metabolism and neurotransmitters should theoretically precede structural changes.

The above described functional imaging studies of meditation suggest that there is a network associated with such practices that includes changes in the attentional system of the brain including the prefrontal cortex, cingulate gyrus, and superior parietal lobes. There also appears to be changes of activity in the limbic areas such as the amygdala, hippocampus, and thalamus. An analysis of functional changes will have implications for understanding complex

neurocognitive and affective tasks. Such findings can also assist toward focusing future clinical studies of meditation techniques on specific disorders known to be associated with the same nervous system structures.

We have chosen fMRI imaging of cerebral blood flow for several reasons. We have increasingly utilized fMRI in our studies and fMRI can provide multiple scans on subjects in the same session. This allows for the ability to compare meditation to baseline as well as to other control conditions.

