4.2 Trial Design

Overall:

This study will initially utilize DaTSCAN and fMRI in healthy subjects within one month of entering a meditation retreat program. In addition, they will complete a variety of questionnaires and scales to assess their psychological status. They will then undergo the retreat and will return within one week of completing the retreat to repeat the scans and questionnaires. Thus, they will receive 2 DaTSCAN scans and 2 fMRI scans over the course of the study.

Time	Procedure
09:00 a.m.	Subject arrival. Review informed consent procedures.
09:30 a.m.	beta-HCG (if necessary)
09:45 a.m.	SSKI (Lugol's solution)
10:00 a.m.	Insert i.v. catheter
10:15 a.m.	Inject DaTSCAN
11:00 a.m.	Subject may take a break for 4 hours during which several
	qualitative scales will be performed
01:15 p.m.	Begin SPECT imaging
02:15 p.m.	SPECT scan completed
02:30 p.m.	Study completed

Approximate Timeline for DaTSCAN SPECT

Medical assessment procedures. A trained physician will take a detailed medical history on each subject and perform a standardized review. Structured physical, neurological, and psychological examinations will be performed. A set of clinical laboratory studies may be used to screen potential subjects with benign histories and normal physical examinations. A urine test for pregnancy will be performed in all women of childbearing potential. Female subjects with negative pregnancy tests will be enrolled.

Quantifying subjective phenomena. This protocol will add the administration of a number of neuropsychological tasks, psychological inventories, and spiritual scales at the time of imaging. These tests and questionnaires should take approximately two hours to complete, and many have already been widely used in both control and patient populations. These well established tests

were originally validated in large populations of people, and have since been used extensively in both clinical and research settings. Our lab has its own normative data base, which has been generated for people of all age ranges. The battery may include the following tests:

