The traditional method for analyzing brain fMRI and SPECT images involves the ROI method described above. However, it has long been known that ROI definition, particularly on functional images, is time-consuming, subjective and prone to operator bias. Small regular ROI's are capable of resolving localized focal changes between images, although they are subject to a loss of specificity due to the problems associated with multiple comparisons. Alternatively, large ROI's encompassing an entire brain structure may dilute small activation foci, with a subsequent loss of sensitivity. Unless a study is very strongly hypothesis driven, and comparisons between images are only being made in highly specific regions, ROI analysis lacks the power to accurately distinguish regional variations between a set of images. The solution to this problem has been the development of pixel-based statistical analyses, where the regions are effectively reduced to single pixels (Acton 1998). This method can also be utilized to observe changes in structures not included as part of the ROI analysis.

Therefore, SPM2 software (Wellcome Department of Cognitive Neurology, London, UK) will also be performed in which the image volumes of transverse slices will be made compatible with SPM by creation of usable headers for the images. To begin, a file will be created for each image that contains data on image size, number of slices, pixel depth, maximal pixel value, and voxel size. SPM analysis then requires 1) spatial normalization of all images into the same stereotactic space, 2) smoothing, and 3) statistical parametric comparisons. Spatial Normalization will begin by having the scans from each individual subject will be coregistered to each other, using a rigid-body transformation. To correct for global brain shape differences, the individual MRI volume acquisitions will be transformed into a standard 3D space (MNI, provided by SPM). The images will be coregistered to a MNI atlas template, using affine transformations and nonlinear warping ($7 \times 8 \times 7$ basis functions). The resulting spatially normalized images had isotropic voxels of size 2 mm. The normalized images will be smoothed by convolving with an isotropic FWHM 12 mm Gaussian kernel that allows the subsequent voxel-by-voxel analysis. This reduces the effects of image noise and conditions the data for subsequent statistical tests performed in SPM.

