Groups of images will be compared voxel-by-voxel using SPM (Friston 1995). Statistically significant differences between sets of data will be assessed at each voxel with a threshold of P < 0.001. To correct for correlated multiple comparisons, clusters of voxels which survive this threshold will be assessed further using the theory of random Gaussian fields (Friston 1994, 1995b; Worsley 1994), which calculates the significance of clusters based on their peak height and spatial extent. With this technique, differences in blood flow between and within groups will be assessed, and statistic images generated showing significant regional differences between groups. The meditation or activation state can be modeled by a simple one-way analysis of covariance (ANCOVA) with a group effect (the activation) combined with a nuisance or confounding effect (global or reference region activity) to produce the observed data. Other covariables such as age, and psychological measures, can also be included in the statistical

analysis. The cerebral structures will be identified by their Talairach coordinates (Talairach 1988).

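### The only model named for the voxelwise maps, a one-way ANCOVA in 9.1, has no subject term, although every subject is imaged repeatedly

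*Combined protocol and SAP*

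**What the plan says.** The study has one non-randomized cohort (4.8). Section 4.2 describes scanning before and after the retreat: "Thus, they will receive 2 DaTSCAN scans and 2 fMRI scans over the course of the study". Under MR image acquisition, 4.2 adds that brain function is examined both at rest and during meditation. Section 2.2 explains the choice of fMRI partly on the ground that "fMRI can provide multiple scans on subjects in the same session".

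The SPM part of 9.1 opens by referring to both modalities ("The traditional method for analyzing brain fMRI and SPECT images involves the ROI method described above") and presents voxelwise mapping as an addition to the region-of-interest (ROI) analysis. Its model sentence reads "The meditation or activation state can be modeled by a simple one-way analysis of covariance (ANCOVA) with a group effect (the activation"). The only other term in that sentence is a nuisance for global or reference-region level. The optional extras are listed as follows: "Other covariables such as age, and psychological measures, can also be included in the statistical". Subject is not among them. The same paragraph says that "differences in blood flow between and within groups will be assessed" and speaks of "statistic images generated showing significant regional differences between groups".

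The documents name no paired test, subject block, repeated-measures model or random effect. The primary outcome (4.2, SPECT acquisition and analysis) is the SERT and DAT binding ratio by ROI. For ROIs, 9.1 says only that ratios are compared across scans, without a test.

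**The concern.** The main contrasts, before against after and rest against meditation, are made within the same people. A one-way model has one factor, here the state. Stable regional differences between subjects then have nowhere to go but the error term. With one image per state, this makes the test too cautious and real change can be missed. If several images per state enter as replicates, images rather than subjects become the unit of analysis, and the test can become too liberal. The random-field cluster step in 9.1 starts from the voxel statistics, so it does not repair a wrong voxel-level standard error.

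**Working it through.** **Inputs from the plan.** 9.2 gives a 10% mean change, a 15% standard deviation, 25 subjects and two-sided 0.05. It does not say whether 15% is the SD of the change or of a single scan, so both readings are shown.

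**Assumed.** The within-subject correlation rho, the number of images per state and the fMRI variance components are not in the documents.

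**The plan's own figure.** 9.2 states 80% power at 25 subjects with a two-group t-test. With d = 10/15 = 0.667, that test needs 37 per group and has 64% power at 25 per group. A paired test with 15% as the SD of change needs 20 subjects and has 89% power at 25. Neither reproduces the statement. That is a separate matter; only the 10% and 15% are used below.

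**One image per subject per state.** Let s be the SD of one image.
- Standard error without a subject term: s·sqrt(2/n).
- True standard error of the mean change: s·sqrt(2(1-rho)/n).
- Ratio: 1/sqrt(1-rho) = 1.20, 1.41 and 1.83 at rho 0.3, 0.5 and 0.7.

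If 15% is the SD of change, s = 15/sqrt(2(1-rho)), which is 12.7, 15.0 and 19.4. The two readings therefore coincide at rho 0.5. Simulated results at n = 25 and nominal 5%:

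| rho | Type I error, no subject term | Power if 15% is SD of change: unpaired / paired | Power if 15% is SD per scan: unpaired / paired |
|---|---|---|---|
| 0.3 | 2.0% | 82% / 89% | 66% / 77% |
| 0.5 | 0.7% | 69% / 89% | 69% / 89% |
| 0.7 | 0.1% | 39% / 89% | 73% / 98% |

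At the plan's voxel threshold of 0.001, with 15% as the SD of change, paired power is 37%. Unpaired power is 8% at rho 0.5 and 0.8% at rho 0.7.

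**With the global covariate.** Fitting state plus a simulated global covariate, as 9.1 describes, gives type I error of 0.021, 0.009 and 0.001 without a subject term, against 0.045 to 0.053 with one. With 15% as the SD per scan, adding the subject term raises power from 0.65 to 0.74, 0.67 to 0.87 and 0.71 to 0.98. In this simulation the covariate does not stand in for the subject term.

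**Several fMRI images per state, k, pooled as replicates.** Assume subject SD = noise SD = 1 and a between-subject SD of the state effect of 0.5, with no mean effect.
- True variance of the difference: (0.25 + 2/k)/25.
- Variance the pooled test assumes: the image variance is 2 in one state and 2.25 in the other, average 2.125, giving 2 × 2.125/(25k) = 4.25/(25k).
- Ratio true/assumed: (0.25k + 2)/4.25, which equals 1 at k = 9.

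Below about 9 images per state the pooled test is conservative; above that it is anti-conservative. Simulation agrees: the false-positive rate at nominal 5% is below 5% up to about 8 images, about 6–7% at 10 and about 25% at 40. A paired test on subject means stays near 5%. Other variance shares move the crossover. With subject 0.5, subject-by-state 0.2 and residual 0.3, the rate is 0.007, 0.023, 0.071 and 0.206 at 1, 2, 4 and 10 images. With no subject-by-state variance (0.5, 0, 0.5) it stays below 0.01 throughout.

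**The case against.** The wording is permissive: the state can be modeled this way. The paragraph also promises comparisons within groups, and a group there may simply mean a set of images. A reader might infer that the plan commits to treating images as independent; the text never says so. That stands as a limit on the claim. But no alternative model is offered, and a reference to within-group differences does not supply a subject term, so an analyst following 9.1 has only the one-way model.

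A reader might also infer that the primary SPECT result is affected. It is not governed by this sentence. The primary outcome is an ROI ratio with no named test, so the gap there is omission. The ANCOVA sentence also directly follows one about blood flow. SPECT maps come in only through the opening of the SPM part, as an additional analysis.

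Finally, a reader might infer that SPECT maps must miss change and fMRI maps must declare too much. The SPECT loss depends on rho and on the meaning of the 15%, and at rho 0.3 it is modest. The fMRI inflation needs enough images per state pooled as replicates and subjects who differ in their response. The remark in 2.2 about multiple scans is background on the choice of method and does not say that several images per state enter the group model.

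**Conclusion.** The point holds for the voxelwise maps. The design is within subject, and the only model named for the maps omits the subject. Taken literally, it gives wrong standard errors whenever a subject's images are correlated. With one image per state and positive correlation, the direction is certain (too conservative) and the size is conditional: from 82% against 89% power at rho 0.3 to 39% against 89% at rho 0.7 if 15% is the SD of change, or 66% against 77% to 73% against 98% if it is the SD per scan. For fMRI the direction cannot be fixed from the documents. All simulated sizes are for a single voxel or region and rest on assumed correlations and variances. Except for the 0.001 figures, they use the nominal 5% level; none includes the cluster step. Because 9.2 calls the study exploratory and the maps are additional to the primary ROI ratios, this should be corrected, but it does not by itself invalidate the primary comparison.

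**What to change.** Replace the one-way ANCOVA sentence in 9.1.
- **SPECT maps:** one pre and one post image per subject in a paired (subject-blocked) model, keeping the nuisance term if wanted.
- **fMRI:** estimate one contrast image per subject per session at a first level, then take these to a second-level paired pre/post test, so that subjects are the replicates.
- **ROI binding ratios:** name the same paired pre/post comparison, since the ROI part of 9.1 names none.

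The wording about differences between groups should be changed to pre/post or state differences, so that it matches a single cohort. The cost is a few sentences and a different design choice in software already planned. No new subjects, scans or data are needed.

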9.2 Number of Subjects

This is an exploratory study and thus a full power analysis will be based upon the determination of the effect size obtained from this data. However, preliminary analyses of our studies in other neuropsychological states of subjects as well as in differences in our serotonin and dopamine transporter binding differences between various populations and treatment groups, we conservatively estimate that the mean differences/changes in these values are approximately 10% with a 15% standard deviation. A sample size of 25 subjects would have 80% power to detect such an effect size using a two group t-test with a 0.05 two-sided significance level. For sample size based on correlation analysis, we typically have considered an R=0.5 to be of clinical importance and have frequently obtained such as measure in comparing various neuropsychological test results to imaging measures. A power calculation to detect a correlation between imaging and neuropsychological measures for an R=0.5 would require a sample size of 30 subjects. Thus, given our usual difference and standard deviation between pre and post studies as well as correlational analysis, a sample size of 25 subjects seems appropriate.

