- 6. Previous brain surgery or intracranial abnormalities they may complicate interpretation of the brain scans (e.g., stroke, tumor, vascular abnormality).
- 7. Pregnancy.
- 8. Allergy to iodine or shellfish.
- 9. Concurrent participation in another research protocol that might affect the outcome of this study as determined by the principle investigator.

b. Sample Size

We anticipate recruiting up to 30 subjects for the study.

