5.3 Subject Withdrawal Criteria

- 5.3.a. When and How to Withdraw Subjects
 - a. The subject cannot tolerate lying still in the scanner due either to pain or claustrophobia that cannot be corrected by pain medications or sedation of the subject.
 - b. The subject develops a systemic allergic reaction.
 - c. The subject experiences significant hemodynamic compromise that requires medication and hospitalization.
 - d. The subject is free to withdraw at any time they choose without affecting their continuing care for their illness.
 - e. If any of the above criteria are met, the subject will no longer undergo DaTSCAN scans. A discontinuation form will be completed and placed in the subject's binder.
 - f. If a subject is withdrawn, they will be requested to continue follow up only if they experienced an adverse event as per the protocol.

5.3.b. Type and Timing of Data Collection

1. All data will be collected at the time of the scanning procedure and at the time that it is determined that the subject is to be withdrawn from the study.

2. Any data from the scan will be removed from the data analysis due to possible confounding of the actual scan data related to the subject's inability to complete the scan.

3. Clinical data that can be used as part of the study can continue to be evaluated and the subject may continue with a clinical arm of the trial. However, the subject's data will not be included in any analysis of DaTSCAN or fMRI scan findings and their relationship to clinical variables.

5.3.c. Subject Replacement

Subjects that cannot or do not complete the study will be replaced in order to obtain enough data. If a subject experiences a serious adverse event directly related to the DaTSCAN or fMRI scan, then no further subjects will be recruited until the cause of the event is determined and it is ensured that no future such events will occur.

5.3.d. Follow up of Withdrawn Subjects

1. They will continue to have medical follow up as necessary.

6. Treatment of Subjects

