9.4 Criteria for Termination of the Trial

The study will be terminated only if there are serious adverse events that occur in the subjects. Otherwise, we anticipate terminating the trial after 25 subjects are recruited and studied.

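### The 80% power claimed for 25 subjects does not follow from the two-group t-test named in section 9.2, the design is paired, and 25 is below the 30 that section 9.2 requires for its correlation aim

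*Combined protocol and SAP*

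**What the plan says.** Section 9.2 is the only justification of the sample size. It first calls the study exploratory. It then draws on earlier work, partly in other populations and treatment groups, to assume that "the mean differences/changes in these values are approximately 10% with a 15% standard deviation". From this it concludes: "A sample size of 25 subjects would have 80% power to detect such an effect size using a two group t-test", at a two-sided 0.05 level.

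A second calculation covers correlations between imaging and neuropsychological measures: power "for an R=0.5 would require a sample size of 30 subjects". The power behind that 30 is not stated. The section closes by calling 25 appropriate "given our usual difference and standard deviation between pre and post studies as well as correlational analysis".

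The other relevant places are:

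- Section 9.4: "we anticipate terminating the trial after 25 subjects are recruited and studied".
- Section 5.1b: "We anticipate recruiting up to 30 subjects for the study".
- Section 5.3.c: "Subjects that cannot or do not complete the study will be replaced in order to obtain enough data".
- Section 4.2, on each subject: "Thus, they will receive 2 DaTSCAN scans and 2 fMRI scans over the course of the study".
- Section 2.6 gives a single population, healthy controls, and section 4.8 says there is no randomization.

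**The concern.** There are three faults, all in section 9.2.

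1. Every input to the first power statement is given, so it can be recomputed, and the stated 80% does not come out.
2. The test named compares two independent groups. The trial has one group measured twice.
3. The section derives 30 for the correlation aim and then adopts 25 for both aims.

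A reader therefore cannot tell what power the study has for its pre/post comparison, because that depends on what the 15% SD describes. For the correlations, which section 4.2 plans between the imaging data and measures of cognition, mood and spirituality, the adopted size is below the plan's own requirement.

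**Working it through.** **Inputs.** From section 9.2: difference or change 10%, SD 15%, two-sided 0.05, n = 25, stated power 80%, R = 0.5 with n = 30. The standardized effect is d = 10/15 = 0.667.

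**1. The plan's figure with the plan's test.** For a two-group t-test the noncentrality is d / √(1/n₁ + 1/n₂) with n₁ + n₂ − 2 degrees of freedom. Power is the probability that the noncentral t falls beyond the critical value.

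| Reading of 25 | Noncentrality | df | Critical t | Power |
|---|---|---|---|---|
| 25 per group | 0.667/√(2/25) = 2.357 | 48 | 2.011 | 63.7% |
| 25 in total (12 and 13) | 0.667/√(1/12 + 1/13) = 1.665 | 23 | 2.069 | 35.8% |
| 36 per group | 2.828 | 70 | 1.994 | 79.7% |
| 37 per group | 2.867 | 72 | 1.993 | 80.8% |

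A one-sided test does not rescue the figure (75.1% at 25 per group, 48.9% at 25 in total). Nor does the normal approximation (65.4% and 38.5%, two-sided). No two-group reading gives 80%.

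**2. The test that fits the design.** For a paired t-test the noncentrality is (mean change / SD of change) × √n with n − 1 degrees of freedom.

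*If 15% is the SD of the within-subject change:*

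| n | Noncentrality | Power |
|---|---|---|
| 20 | 0.667 × √20 = 2.981 | 80.7% |
| 25 | 0.667 × √25 = 3.333 | 89.2% |
| 30 | 0.667 × √30 = 3.651 | 94.2% |

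With 25 subjects, power stays at or above 80% as long as the SD of change is no more than 17.1%.

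*If 15% is the SD of a single scan,* the SD of change is 15 × √(2(1 − ρ)), where ρ is the pre/post correlation. The documents give no ρ, so the values below are assumptions (n = 25).

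| Assumed ρ | SD of change | Power |
|---|---|---|
| 0 | 21.2% | 62% |
| 0.2 | 19.0% | 72% |
| 0.3 | 17.7% | 77% |
| 0.35 | 17.1% | 80% |
| 0.5 | 15.0% | 89% |

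The stated 80% comes out only at a correlation near 0.35, which the plan does not mention.

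**3. The correlation aim.** By Fisher's z, n = ((z for two-sided 0.05 + z for power) / atanh R)² + 3. At an assumed 80% power this is ((1.960 + 0.842)/0.5493)² + 3 = 29.01, rounded up to 30. The plan's 30 therefore reproduces, which makes 80% the likely target.

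Power at a given n is Φ(0.5493 × √(n − 3) − 1.960):

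- n = 25: Φ(2.576 − 1.960) = Φ(0.617) = 73.1%. Simulating the t-test of the correlation gives about 75%.
- n = 30: Φ(2.854 − 1.960) = Φ(0.894) = 81.4%. Simulation gives about 83%.

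The smallest correlation with 80% power at n = 25 is tanh(2.802/√22) = 0.535.

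**The case against.** The strongest reply is that the two-group figures describe a trial nobody plans. Nothing splits the cohort 12 and 13, and 25 per group would need 50 subjects. Section 9.1 uses the word group for sets of images and for the activation effect, so the test named in 9.2 may be loose wording for pre versus post scans. The closing sentence of 9.2 refers to pre and post studies, which favours reading 15% as the SD of change. Power is then 89% and 25 is more than enough. This stands as a limit on the consequence: the pre/post aim is not shown to be underpowered. It does not rescue the text, because the paired reading gives 89% and not 80%, and the SD is also said to draw on differences between populations and treatment groups.

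The study also calls itself exploratory, 9.4 only anticipates stopping at 25, and 5.1b allows up to 30. These points lower the weight. They do not remove the conflict: a specific test, level and power are still asserted, and a recruitment ceiling is not a target. Correlation is not among the endpoints in 4.1, although the first two objectives in section 3 concern associations.

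Finally, the 80% target for the correlation is inferred, and the 89% applies to one binding ratio tested at 0.05. Section 4.2 makes both the serotonin and dopamine transporter (SERT and DAT) ratios primary. If the level were halved to 0.025 for two ratios, paired power at n = 25 would be 82%. Both qualifications are fair and are carried into the fix.

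**Conclusion.** The concern holds. As written, the power statement in 9.2 is wrong for the test it names (64% or 36% against 80%), and that test does not match a single-cohort pre/post design. The correct figure for the pre/post aim is 89% if 15% is the SD of change. If 15% is a single-scan SD, it runs from 62% to 89% over assumed correlations of 0 to 0.5. So 25 may well be adequate for that aim, but the plan does not show it.

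The conflict between 30 and 25 is in the text itself. Its cost is modest: about 73–75% power for R = 0.5, against an inferred target of 80%. This should be fixed as a correction of the stated basis; it is not evidence that the study cannot answer its questions.

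**What to change.** 1. **Section 9.2, pre/post aim.** Replace the two-group sentence with a paired calculation that defines the 15%. If it is the SD of the within-subject change, suitable wording is: 25 subjects give 89% power (20 give 81%) to detect a 10% mean change in one prespecified binding ratio, paired t-test, two-sided 0.05, without multiplicity adjustment. If it is a single-scan SD, state the assumed pre/post correlation and the power that results.
2. **Sections 9.2 and 9.4, correlation aim.** Either state that 25 subjects give about 73–75% power for R = 0.5, or align both sections on 30. If 30 is chosen, say in 5.1b whether the ceiling counts replaced subjects. Thirty complete pairs under a ceiling of 30 leave no room for the replacements in 5.3.c.
3. **Section 9.1 (secondary).** No paired test is named. Region-of-interest ratios are only said to be compared across scans, and the one model written out, a one-way analysis of covariance offered as an option, lists no subject term. Name a paired t-test for the ratios and a voxel-wise model with subject as a block factor, keeping the global or reference-region covariate.

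**Cost.** Wording in 9.2 and 9.4 and a sentence in 9.1, with no extra subjects if the correlation power is restated at 25. Choosing 30 adds five completers, each with two SPECT and two fMRI scans: ten more of each.
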